6. TREATMENT AND/OR IMAGING PLAN

6.1 Agent Administration

Treatment will be administered on an inpatient basis. Reported adverse events and potential risks are described in Section 10. Appropriate dose modifications are described in Section 7

Arm A Regimen Description					
Agent	Premedications; Precautions	Dose	Route	Schedule	Cycle Length
Neoral, Investigational, Generic Acceptable,	NA	2.5 mg/kg	PO	BID	7 days

N=50 Patients					

Arm B Regimen Description					
Agent	Premedications; Precautions	Dose	Route	Schedule	Cycle Length
None*, N= 25 Patients	NA	NA	NA	NA	7 days

*Note: The PI has undertaken thorough discussions with the sponsor and generation of placebo capsules is not feasible for the timing of this study.

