6.2.1.2 **Cytochrome P450 System:** Cyclosporine is extensively metabolized by CYP 3A isoenzymes, in particular CYP3A4, and is a substrate of the multidrug efflux transporter P-glycoprotein. Various agents are known to either increase or decrease plasma or whole blood concentrations of cyclosporine usually by inhibition or induction of CYP3A4 or P-glycoprotein transporter or both. Compounds that decrease cyclosporine absorption such as orlistat should be avoided. Appropriate Neoral dosage adjustment to achieve the desired cyclosporine concentrations is essential when drugs that significantly alter cyclosporine concentrations are used concomitantly.

6.2.1.3 **HIV protease inhibitors** (e.g., indinavir, nelfinavir, ritonavir, and saquinavir) are known to inhibit cytochrome P-450 3A and thus could potentially increase the concentrations of cyclosporine, however no formal studies of the interaction are available. Care should be exercised when these drugs are administered concomitantly.

6.2.1.4 **Grapefruit, grapefruit juice, pomegranate, and orange juice** affect metabolism, increasing blood concentrations of cyclosporine, thus should be avoided.

1. Drugs That Increase Cyclosporine Concentrations

Calcium Channel Blockers	Antifungals	Antibiotics	Glucocorticoids	Other Drugs
diltiazem	fluconazole	azithromycin	methylprednisolone	Allopurinol
nicardipine	itraconazole	clarithromycin		Amiodarone
verapamil	ketonazole	erythromycin		Bromocriptine
	voriconazole	quinupristin/ dalfopristin		colchicine
				danazol
				imatinib
				metoclopramide
				nefazodone
				oral contraceptives

6.2.1.5 **Drugs/dietary supplements that decrease cyclosporine concentrations** include the following agents:

6.2.1.5.1 Bosentan: Coadministration of bosentan (250 to 1000 mg every 12 hours based on tolerability) and cyclosporine (300 mg every 12 hours for 2 days then dosing to achieve a Cmin of 200 to 250 ng/mL) for 7 days in healthy subjects resulted in decreases in the cyclosporine mean dose-normalized AUC, Cmax, and trough concentration of approximately 50%, 30%, and 60%, respectively, compared to when cyclosporine was given alone (See also Effect of Cyclosporine on the Pharmacokinetics and/or Safety of Other Drugs or Agents). Coadministration of cyclosporine with bosentan should be avoided.

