6.2.2.4 Colchicine: There are reports on the potential of cyclosporine to enhance the toxic effects of colchicine such as myopathy and neuropathy, especially in patients with renal dysfunction. Concomitant administration of cyclosporine and colchicine results in significant increases in colchicine plasma concentrations. If colchicine is used

concurrently with cyclosporine, a reduction in the dosage of colchicine is recommended.

6.2.2.5 HMG-CoA reductase inhibitors (statins): Literature and postmarketing cases of myotoxicity, including muscle pain and weakness, myositis, and rhabdomyolysis, have been reported with concomitant administration of cyclosporine with lovastatin, simvastatin, atorvastatin, pravastatin, and, rarely fluvastatin. When concurrently administered with cyclosporine, the dosage of these statins should be reduced according to label recommendations. Statin therapy needs to be temporarily withheld or discontinued in patients with signs and symptoms of myopathy or those with risk factors predisposing to severe renal injury, including renal failure, secondary to rhabdomyolysis.

6.2.2.6 Repaglinide: Cyclosporine may increase the plasma concentrations of repaglinide and thereby increase the risk of hypoglycemia. In 12 healthy male subjects who received two doses of 100 mg cyclosporine capsule orally 12 hours apart with a single dose of 0.25 mg repaglinide tablet (one-half of a 0.5mg tablet) orally 13 hours after the cyclosporine initial dose, the repaglinide mean Cmax and AUC were increased 1.8 fold (range: 0.6 to –3.7 fold) and 2.4 fold (range 1.2 to 5.3 fold), respectively. Close monitoring of blood glucose level is advisable for a patient taking cyclosporine and repaglinide concomitantly.

6.2.2.7 Ambrisentan: Coadministration of ambrisentan (5 mg daily) and cyclosporine (100 to 150 mg twice daily initially, then dosing to achieve Cmin 150 to 200 ng/mL) for 8 days in healthy subjects resulted in mean increases in ambrisentan AUC and Cmax of approximately 2-fold and 1.5-fold, respectively, compared to ambrisentan alone. When coadministering ambrisentan with cyclosporine, the ambrisentan dose should not be titrated to the recommended maximum daily dose

6.2.2.8 Anthracycline antibiotics: High doses of cyclosporine (e.g., at starting intravenous dose of 16 mg/kg/day) may increase the exposure to anthracycline antibiotics (e.g., doxorubicin, mitoxantrone, daunorubicin) in cancer patients.

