7. DOSING DELAYS/DOSE MODIFICATIONS

- 7.1.1 The dose of Neoral is 2.5mg/kg PO BID, based on the renal transplant dose, and Neoral will be administered for 7 days.
- 7.1.2 A blood cyclosporine trough level will be obtained on day 3 to avoid toxicity due to high concentrations. If this level is greater than 250 ng/ml, the Neoral dose will be decreased by 25-50%. If the level is 250 ng/ml or less, no modifications will be made.
- 7.1.3 Cyclosporine trough levels will be also obtained on day 6 and day 9. If this level is greater than 250 ng/ml on day 6 the Neoral dose will be decreased by 25-50% for the rest of the study period (7 days).

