Written Informed Consent								
Assign Screening Number								
Complete Medical History								
Demographics								
Inclusion/Exclusion Criteria Review								
WHO COVID-19 Severity Scale	X	X	X	X	X	X	X	
Assign Enrollment Number								
Complete Physical Examination	X	X	X	X	X	X		
Vital Signs (BP, HR, RR, Temp, SpO ₂)	X	X	X	X	X	X		
FIO ₂ Assessment	X	X	X	X	X	X		
Pregnancy Test for Female Patients								
Cyclosporine Administration								
12-Lead ECG								
Chest X-ray								
BMP	X	X	X	X	X	X		
LFTs	X	X	X	X	X	X		
CBC	X	X	X	X	X	X		
ANC	X	X	X	X	X	X		
Absolute Lymphocyte Count	X	X	X	X	X	X		
Ferritin	X	X	X	X	X	X		
D-Dimer	X	X	X	X	X	X		
CRP	X	X	X	X	X	X		
LDH	X	X	X	X	X	X		
Magnesium	X	X	X	X	X	X		
Phosphorus	X	X	X	X	X	X		
PT/PTT	X	X	X	X	X	X		
Cyclosporine Level ³								
SARS-CoV-2 PCR				X		X	X	
AE Assessment	-----Continuous Monitoring from Signing of the Informed Consent-----►							
Concomitant Medications/Therapies	-----Continuous Monitoring from Signing of the Informed Consent-----►							

ANC =Absolute neutrophil count; BMP =basic metabolic panel; BP = blood pressure; CBC = complete blood count; CRP = c-reactive protein; ECG = Electrocardiogram; FIO₂ = oxygen requirement; HR = heart rate; LDH = lactate dehydrogenase; LFTs = liver function tests; PT = prothrombin time; PTT = partial thromboplastin time; RR = respiratory rate; SpO₂ = oxygen saturation; WHO = World Health Organization.

¹Treatment assessments will be performed every 24±6 hours. Treatment is Neoral for 7 days and will begin as an inpatient and will be discontinued if the patient is discharged before the 7d course is completed. If the patient is discharged before 7 days, the patient will not undergo any assessments until the first outpatient visit.

²Follow up will be performed every 24±6 hours while inpatient. Once patient is discharged, follow up will be at days 14±3 days, 28±3 days, and 60±3 days either by in person clinic visit or telemedicine visit.

³Cyclosporine trough levels will be checked on day 3. If >250 mg/ml, the dose will be decreased by 25-50%. Additional levels will be at the discretion of treating physicians but will be performed on day 6 and day 9 if the participant is an inpatient.

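### Table 1 footnote 3 gives the day-3 cyclosporine dose-reduction threshold in mg/ml; Section 7 gives it in ng/ml, and the footnote is wrong

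*Combined protocol and SAP*

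**What the plan says.** Section 6.1 tells the reader where the dosing rules are: "Appropriate dose modifications are described in Section 7". Section 7.1.1 sets the regimen: "The dose of Neoral is 2.5mg/kg PO BID, based on the renal transplant dose, and Neoral will be administered for 7 days". Section 7.1.2 then gives the day-3 rule, "If this level is greater than 250 ng/ml, the Neoral dose will be decreased by 25-50" per cent, and its complement, "If the level is 250 ng/ml or less, no modifications will be made". Section 7.1.3 repeats the threshold for the second level: "If this level is greater than 250 ng/ml on day 6 the Neoral dose will be decreased by 25-50" per cent.

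Footnote 3 to Table 1 in Section 8 restates the day-3 rule for users of the calendar: "If >250 mg/ml, the dose will be decreased by 25-50" per cent.

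The protocol quotes cyclosporine troughs in two other places, both in the drug-interaction text of Section 6.2. Section 6.2.1.5.1 (bosentan) has "then dosing to achieve a Cmin of 200 to 250 ng/mL" and Section 6.2.2.7 (ambrisentan) has "then dosing to achieve Cmin 150 to 200 ng/mL".

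**The concern.** Section 7.1.2 and footnote 3 state one rule in two units, and both cannot be right. Section 7.1.2 says that the day-3 level is taken to protect patients from toxicity caused by high drug levels, so the number that triggers the reduction is a safety threshold. The calendar is a table that site staff work from, and its footnote should give the same trigger as the section that governs dosing. Applied literally, the footnote would leave every patient on full dose whatever the trough.

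**Working it through.** **1. The two statements side by side**

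| Element | Section 7.1.2 | Table 1 footnote 3 |
|---|---|---|
| Day | 3 | 3 |
| Number | 250 | 250 |
| Unit | ng/ml | mg/ml |
| Action | reduce by 25-50% | reduce by 25-50% |

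Only the unit differs, by one letter.

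**2. Size of the difference**

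1 mg = 1,000,000 ng, so 250 mg/ml = 250 × 1,000,000 = 250,000,000 ng/ml. Ratio to the Section 7 threshold: 250,000,000 / 250 = 1,000,000.

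**3. Which unit is right: internal evidence**

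- Section 7, the section named in 6.1 for dose modifications, uses ng/ml three times: twice in 7.1.2 and once in 7.1.3.
- The two troughs in Section 6.2 (200 to 250 and 150 to 200) are in ng/mL, and a threshold of 250 ng/ml sits at the top of that range.
- The count is therefore five statements in ng/ml and one in mg/ml.

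**4. Which unit is right: could 250 mg/ml occur?**

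This is a deliberate overestimate. It assumes that every dose is fully absorbed, stays in the blood and is never eliminated. The documents give no blood volume, so I assume 50 to 80 ml/kg.

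Ceiling concentration = (number of doses × 2.5 mg/kg) / blood volume (ml/kg).

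| Doses counted | Total dose | At 80 ml/kg | At 50 ml/kg | Shortfall against 250 mg/ml |
|---|---|---|---|---|
| 4 (days 1 and 2, taking the trough before the first day-3 dose) | 4 × 2.5 = 10 mg/kg | 10/80 = 0.125 mg/ml | 10/50 = 0.20 mg/ml | 250/0.125 = 2,000-fold to 250/0.20 = 1,250-fold |
| 14 (full 7 days, twice daily) | 14 × 2.5 = 35 mg/kg | 35/80 = 0.4375 mg/ml | 35/50 = 0.70 mg/ml | 250/0.4375 = 571-fold to 250/0.70 = 357-fold |

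Even the whole course held in the blood at once would fall short of the printed threshold by a factor of at least 357.

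**The case against.** The best counter-argument is that this is proofreading. The governing rule is stated correctly and completely in Section 7, including what to do at or below the threshold. The footnote has the same day, number and percentage, so a reader can see at once which unit was meant. A clinician would have to disregard Section 7 and accept an impossible concentration before any patient was affected. That stands, and it is why the point is minor. It does not make the footnote right, and no other text corrects it.

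A second argument is that the letter may have been misread when the text was taken from the PDF. Parts of Table 1 are visibly damaged in the text available here, and the five readings of ng/ml all come from body text, not from a table footnote. This cannot be ruled out from the extracted text. The footnote is, however, a complete and legible sentence, and the same unit was read as ng/ml everywhere else. I regard a misread as unlikely, but the source PDF should settle it.

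A third argument is that the blood-volume calculation proves something nobody disputes. That is fair: the factor of 1,000,000 and the internal evidence are enough, and the calculation only confirms that the literal threshold could not be met.

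**Conclusion.** The concern holds as a minor error, with high confidence. As printed, footnote 3 overstates the dose-reduction threshold by a factor of 1,000,000 and could never trigger a reduction. The correct unit is ng/ml. That conclusion rests on the protocol's own statements. The assumed blood volume supports only the unattainability check, and no plausible value would change it.

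Practical impact is modest. Section 7 is consistent and governs. Table 1 also schedules vital signs, a basic metabolic panel and liver function tests on each treatment day. The Table 4 boundaries add trial-level protection, although they pause the trial and do not adjust an individual's dose. The documents do not say how many troughs would exceed 250 ng/ml, so the number of patients who might be affected cannot be given. The sample size, the power, the primary analysis and the Table 4 boundaries do not depend on this threshold.

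**What to change.** Check the letter against the source PDF. If it reads as extracted, change mg/ml to ng/ml in Table 1 footnote 3. Alternatively, remove the threshold from the footnote and cite Section 7, so that the rule is stated once. In that case keep the rest of the footnote, because its condition that the day-6 and day-9 levels apply to inpatients does not appear in Section 7.1.3. The cost is one letter or one cross-reference, with no additional tests and no change to any analysis.

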9. PHARMACEUTICAL INFORMATION

A list of the adverse events and potential risks associated Neoral can be found in Section 10.1.

9.1 IND Agent

9.1.1 Neoral

Availability

Neoral is an investigational agent supplied to investigators by Novartis.

9.1.2 Agent Ordering and Agent Accountability

9.1.2.1 Agent Inventory Records – The investigator, or a responsible party designated by the investigator, must maintain a careful record of the receipt, dispensing and final disposition of Neoral including, strength, formulation and ordering investigator on this protocol.

9.1.3 Investigator Brochure Availability

The sponsor does not have an investigator brochure for Neoral, however the USPI will be available to all investigators

(https://www.accessdata.fda.gov/drugsatfda_docs/label/2019/050715s035,050716s038lbl.pdf)

10. MEASUREMENT OF EFFECT

The primary outcome of this study is the WHO COVID-19 clinical severity scale on day 14. Please, see the Table 2.

Table 2. WHO COVID-19 Ordinal Outcomes Scale

Patient State	Descriptor	Score
Uninfected	No clinical or virological evidence of infection	0
Ambulatory	No limitation of activities	1
	Limitation of activities	2
Hospitalized Mild disease	Hospitalized, no oxygen therapy	3
	Oxygen by mask or nasal prongs	4
Hospitalized Severe Disease	Non-invasive ventilation or high-flow oxygen	5
	Intubation and mechanical ventilation	6
	Ventilation + additional organ support – pressors, RRT, ECMO	7
Dead	Death	8

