8. STUDY CALENDAR

Table 1 Schedule of Study Events (Part 1)

Visit	Screening	Baseline	Treatment ¹							Follow-up ²		
	1	2	3	4	5	6	7	8	9	10		
Study Day	-21 to -1	-2 to 0	1	2	3	4	5	6	7	8	9	10
Written Informed Consent	X											
Assign Screening Number	X											
Complete Medical History	X											
Demographics	X											
Inclusion/Exclusion Criteria Review	X											
WHO COVID-19 Severity Scale	X	X	X	X	X	X	X	X	X	X	X	X
Assign Enrollment Number		X										
Complete Physical Examination	X	X	X	X	X	X	X	X	X	X	X	X
Vital Signs (BP, HR, RR, Temp, SpO ₂)	X	X	X	X	X	X	X	X	X	X	X	X
FIO ₂ Assessment	X	X	X	X	X	X	X	X	X	X	X	X
Pregnancy Test for Female Patients	X											
Cyclosporine Administration			X	X	X	X	X	X	X			
12-Lead ECG	X								X			X
Chest X-ray	X								X			X
BMP	X	X	X	X	X	X	X	X	X	X	X	X
LFTs	X	X	X	X	X	X	X	X	X	X	X	X
CBC	X	X	X	X	X	X	X	X	X	X	X	X
ANC	X	X	X	X	X	X	X	X	X	X	X	X
Absolute Lymphocyte Count	X	X	X	X	X	X	X	X	X	X	X	X
Total Cholesterol	X	X										
Ferritin	X	X	X	X	X	X	X	X	X	X	X	X
D-Dimer	X	X	X	X	X	X	X	X	X	X	X	X
CRP	X	X	X	X	X	X	X	X	X	X	X	X
LDH	X	X	X	X	X	X	X	X	X	X	X	X
Magnesium	X	X	X	X	X	X	X	X	X	X	X	X
Phosphorus	X	X	X	X	X	X	X	X	X	X	X	X
PT/PTT	X	X							X			
SARS-CoV-2 PCR	X											
AE Assessment	Continuous Monitoring from Signing of the Informed Consent-----►											
Concomitant Medications/Therapies	Continuous Monitoring from Signing of the Informed Consent-----►											

ANC =Absolute neutrophil count; BMP =basic metabolic panel; BP = blood pressure; CBC = complete blood count; CRP =c-reactive protein; ECG = Electrocardiogram; FIO₂ = oxygen requirement; HR = heart rate; LDH = lactate dehydrogenase; LFTs = liver function tests; PT = prothrombin time; PTT = partial thromboplastin time; RR = respiratory rate; SpO₂ = oxygen saturation; WHO = World Health Organization.

¹Treatment assessments will be performed every 24±6 hours. Treatment is Neoral for 7 days and will discontinued on the day of discharge if the patient is discharged before the 7d course is completed. If the patient is discharged before 7 days, the patient will not undergo any assessments until the first outpatient visit.

²Follow up will be performed every 24±6 hours while inpatient. Once patient is discharged, follow up will be at days 14±3 days, 28±3 days, and 60±3 days either by in person clinic visit or telemedicine visit.

Table 1 Schedule of Study Events (Part 2)

Visit	Follow-up ²							
	11	12	13	14	15-27	28	60	
Study Day	11	12	13	14	15-27	28	60	

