11.2 Sample Size /Justification

We expect to see higher grades of WHO COVID ordinal clinical scale in control group compared to the CSA treatment group, and propose to use a 1 to 2 randomization in favor of CSA group.

The total sample size of 75 evaluable participants will provide 81% power to reject the null hypothesis that the grade in control group is less than or equal to the CSA group with a 10% one-sided significance level when the true effect size, as measured by the probability that

Control grade is greater than CSA grade, is 0.65 or greater. Sample size and/or power for the various scenarios were calculated using nQuery 8 (StatSols Version 8.5.2.0).

The following provides the rationale for the alternate hypothesis effect size. We have assumed that all participants will be starting in category 4. Based on review of hospital data, about one third of such patients end-up in the ICU and about half of those patients will die. Of the two thirds that do not go to the ICU, most will be discharged in 2 weeks or less. We have therefore hypothesized that at 2 weeks following enrollment, the control group will be distributed as shown in the table 3.

We have hypothesized several scenarios to estimate the sample size needed to detect a CSA effect with reasonable power. We expect the effect of CSA will be to reduce ICU admissions, or to shorten time in the ICU and reduce deaths, so that the fraction in categories 6, 7, and 8 on Day 14 will be reduced and less ill patients will go home earlier, increasing the fraction of 1 and 2's on day 14.

Since the outcome is ordinal, a Wilcoxon rank sum test is used to control (no CSA) and CSA on day 14. The one-tailed null hypothesis is that the distribution of WHO scores is the same in two groups or worse in CSA, and the alternative is that the distribution of WHO scores in the CSA group is shifted lower. The effect size ($P_1 = \Pr(\text{Control} > \text{CSA})$) is the probability that a randomly selected observation from the control group has a score greater than one from CSA group. The null value for P_1 is 0.5 and the closer P_1 to 1, the bigger the effect.

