A sample size of 25 in the control group and 50 in the CSA group will have 81% power to reject the null hypothesis (based on the 8 observable category probabilities for each group shown in table 3) in favor of the alternative hypothesis that an observation in the control group has a higher score on day 14 than an observation in the CSA group using a Wilcoxon (Mann-Whitney) rank-sum test with the type 1 error of 10% one-sided significance level.

Table 3. Scenarios and associated sample size and power.

		At Accrual	Control	CSA Scenario 1 ~50% benefit	CSA Scenario 2 ~40% benefit	CSA Scenario 3 ~30% benefit
8	Death	0	17%	8%	10%	12%
7	Hospitalized, vented, pressors	0	8%	4%	5%	5%
6	Hospitalized w invasive ventilation	0	8%	4%	5%	6%
5	Hospitalized non-invasive ventilation	0	5%	2%	3%	3%
4	Hospitalized on O2	100%	5%	2%	3%	3%
3	Hospitalized not on O2	0	10%	2%	4%	7%
2	Not hospitalized with symptoms	0	24%	39%	35%	32%
1	Not hospitalized with no symptoms	0	23%	39%	35%	32%
Effect Size (P1=Pr(Control>CSA)				0.65	0.61	0.59
Power & sample size ($\alpha=10\%$, 1-tailed)						
	Power with N=25 control, 50 CSA			81%	62%	48%
	Sample size for ~80% power; Ctl:CSA			25:50	45:90	75:150

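### The primary scale lets a day-14 swab separate score 0 from score 1, while the power table has no score 0 and defines scores 1 and 2 differently; pool 0 with 1 and align the labels

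*Combined protocol and SAP*

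**What the plan says.** Section 11.1 makes the WHO ordinal scale at day 14 the primary endpoint and compares the arms by a Wilcoxon rank sum test. Section 11.4.2 assigns each randomised patient a category of Table 2, which runs from 0 to 8. The three lowest scores cover patients who are no longer in hospital:

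- Score 0: "No clinical or virological evidence of infection".
- Score 1: ambulatory, activities not limited.
- Score 2: ambulatory, activities limited.

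Section 5.1 takes virology from nasopharyngeal swabs. Table 1 schedules PCR at day 14, but its second footnote lets follow-up after discharge, within 3 days either side, take place "either by in person clinic visit or telemedicine visit". Sections 4.3 and 11 describe an open-label trial, and section 6.1 rules out placebo capsules. No blinded assessor is described.

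The power statement in section 11.2 is "based on the 8 observable category probabilities for each group shown in table 3". Those categories are scores 1 to 8. Table 3 labels score 1 "Not hospitalized with no symptoms" and score 2 as the same state with symptoms. The expected mechanism is fewer patients in categories 6 to 8, and that "less ill patients will go home earlier, increasing the fraction of 1 and" 2's.

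**The concern.** There are two separate mismatches.

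First, a recovered patient who attends clinic and is PCR-negative meets score 0. The plan does not say how to score the same patient when no swab is taken; score 1 is the natural default. The primary rank would then depend on whether a swab was obtained and not only on clinical state. If the arms differ in how often discharged patients are swabbed, which is possible when everyone knows the allocation, the test responds to that difference.

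Second, the scale that is analysed is not the scale that was powered. Table 3 has no score 0, and it divides 1 from 2 by symptoms where Table 2 uses limitation of activities. A discharged patient with a residual cough and no limitation is 1 under Table 2 and 2 under Table 3. Either division is a judgement made without blinding.

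This part of the scale holds many patients. In Table 3, scores 1 and 2 together hold 23 + 24 = 47% of controls and 39 + 39 = 78% of the Neoral arm in Scenario 1.

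**Working it through.** **Inputs.** Section 11.2 gives 25 control and 50 Neoral patients and one-sided α = 0.10. Table 3, scores 1 to 8:
- Control: 23, 24, 10, 5, 5, 8, 8, 17%.
- Neoral, Scenario 1: 39, 39, 2, 2, 2, 4, 4, 8%.
- Scenarios 2 and 3 likewise from Table 3.

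**1. The plan's own figure.** P1 = Pr(Control > Neoral) + ½ Pr(tie).
- Scenario 1: 0.5466 + ½ × 0.2073 = 0.650. Scenarios 2 and 3: 0.613 and 0.586. The plan states 0.65, 0.61 and 0.59.
- Noether's formula: power = Φ(√[12·c(1−c)·N]·(P1 − 0.5) − z₀.₉₀), with c = 1/3 and N = 75. The root is √200 = 14.14, so Φ(14.14 × 0.150 − 1.282) = 80.0%.
- Simulation of the tie-corrected test gives 82.7%.

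The stated 81% lies between these and is reproduced. It already includes the division between 1 and 2.

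**2. Effect of unequal swabbing when Neoral does nothing.** Both arms follow the control column. Assumptions, none of them in the documents: 70% of score-1 patients are PCR-negative, and patients without a swab are scored 1. Share scoring 0 = 0.23 × 0.70 × (fraction swabbed):
- 90% swabbed: 14.5% at score 0, leaving 8.5% at score 1.
- 50% swabbed: 8.1% and 14.9% (total 23%).
- 25% swabbed: 4.0% and 19.0%.

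The shift in P1 is ½ × 0.23 × (Neoral share at 0 − control share at 0). For 90% v 25% that is ½ × 0.23 × (0.145 − 0.040) = 0.012. Simulated one-sided error, tie-corrected test:

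| Swabbed, Neoral / control | Error |
|---|---|
| equal in both arms | about 10% |
| 90% / 50% | about 12% |
| 90% / 25% | about 13% |
| 50% / 90% | just under 9% |
| 25% / 90% | about 8% |

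With 0 and 1 pooled, these rows all become the control column in both arms, so the error returns to about 10% by construction.

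**3. Effect of unequal rating between 1 and 2, no true effect.** If 20% or 30% of Neoral patients truly at 2 are rated 1, the error is about 13% or 15%. If controls at 1 are also rated 2 at the same rates, it is about 16% or 20%. These rates are assumed too. Pooling 0 with 1 does not remove this route; pooling 0, 1 and 2 does.

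**4. Power with discharged patients as one category.** Simulation, 25:50, Table 3:

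| Scenario | 1 and 2 separate | 1 and 2 pooled |
|---|---|---|
| 1 | 83% | 89% |
| 2 | 65% | 70% |
| 3 | 49% | 52% |

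The gain arises because Table 3 divides discharged patients almost evenly in both arms (23/24 in control; 39/39, 35/35 and 32/32 under Neoral). It depends on that. If about 60% of discharged Neoral patients in Scenario 1 scored 1, separate and pooled power would be about equal (89.6% v 89.1%); above that, keeping them separate gives more power.

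**The case against.** The strongest reply is that nothing here shows actual bias. The documents give no swab rate by arm and no misrating rate, PCR is scheduled at day 14 for both arms, and no passage says that a telemedicine patient goes without a swab. The patient state attached to score 0 is Uninfected, while every entrant has laboratory-confirmed infection. Together with the eight categories of Table 3, this suggests that the planners may not have expected score 0 to be used. All of that stands. It limits the point to exposure to bias, but does not close the gap: section 11.4.2 applies Table 2 in full, and Table 2 includes score 0.

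A reader might infer from the power comparison that discharged patients should form one category in the primary test. The documents do not support going that far. Objective 1.1.1 names the WHO scale, pooling 0 to 2 would tie 78% of the Neoral arm in Scenario 1, and the gain requires no effect among discharged patients. The even divisions in Table 3 may be simple planning allocations. The gain also appears only when the variance is corrected for ties: plain Noether gives 80.0% separate and 79.3% pooled. It belongs in a sensitivity analysis.

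**Conclusion.** The point holds as an exposure to bias and as an inconsistency between two tables. Followed as written, the plan lets the availability of a swab move a recovered patient's primary rank, and it powers a scale that differs from the one analysed, both in its number of categories and in its definitions of 1 and 2.

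The size is modest and has no fixed direction: about 8% to 13% against a nominal 10% under the swab assumptions above, and about 10% if both arms are swabbed and rated alike. A reader might conclude that the primary test is biased; the documents give no differential rate from which that could be shown. A reader might also conclude that the trial falls short of its stated power; it does not, since 81% is reproduced with 1 and 2 kept separate. Score 0 is absent from Table 3, so its effect on power needs an assumption: if 20–60% of discharged patients, or of score-1 patients, scored 0 at the same rate in both arms, Scenario 1 power would be 81–82%.

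**What to change.** In sections 10, 11.1 and 11.4.2:

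1. Pool scores 0 and 1 in the primary Wilcoxon test. PCR then cannot affect the rank, and the analysed scale has the eight categories of Table 3.
2. Use one definition of scores 1 and 2 in Tables 2 and 3.
3. Report the full 0–8 distribution by arm descriptively.
4. Prespecify a sensitivity analysis that pools 0, 1 and 2 as alive and not hospitalised. It is unaffected by the swab and by unblinded rating between 1 and 2. State next to it that its higher power assumes no effect among discharged patients.

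The cost is wording; no new data are needed and the stated sample size stands. The small loss is that virological clearance no longer counts in the primary rank, but PCR positivity at days 14 and 28 remains a secondary endpoint (objective 1.2.3 and section 11.5).
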